STUDY DESIGN	
PART A / Epidemiologic Investigation:
 
The CO-RDP provides a national reference laboratory for CF NTM. NTM respiratory isolates received from CF Care Centers around the U.S. undergo culture, molecular identification, antimicrobial susceptibility, and whole genome sequencing (WGS). Using this approach, the CO-RDP has identified clusters of NTM isolates, defined as highly similar strains at the genomic level, harbored by two or more CF patients who are cared for at the same CF Care Center. These identifications have heightened our concern for potential healthcare-associated NTM acquisition originating from patient-to-patient transmission or a common environmental source within Centers.
 
Using integrated clinical and epidemiological research methods, the HALT NTM retrospective epidemiologic investigation can identify overlaps in source(s) of care between patients with highly similar NTM isolates in a Center. The HALT NTM toolkit facilitates a stepwise process by which individual Centers perform retrospective epidemiologic evaluation of patients identified by the CO-RDP as part of an NTM cluster. HALT NTM is available to the entire CF

	
Foundation Care Network, under a collaborative agreement, to initiate a standardized, independent, confidential, internal NTM outbreak investigation. A control comparison group will also be investigated.
 
PART B / Water Biofilm Collection: Clustered NTM isolates could originate from a shared healthcare water source. Biofilms from healthcare water supplies will be collected and NTM recovered, identified, and sequenced to determine if the respiratory CF NTM strain genotype is similar to those recovered from the healthcare water supply.

PARTICIPANT STUDY DURATION
	
PART A / Epidemiologic Investigation: CF Centers will be eligible for enrollment as NTM clusters are identified by the CO-RDP. The total duration of the study and analysis is 3 years.
 
PART B / Water Biofilm Collection: CF Centers will be eligible for enrollment as NTM clusters are identified by the CO-RDP. The total duration of the study and analysis is 3 years.

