
PRIMARY OBJECTIVE
	
PART A / Epidemiologic Investigation: Our primary objective is to implement a standardized epidemiologic investigation, via the HALT NTM tool kit, in CF Care Centers identified as having clusters of highly similar NTM isolates. We will assess the origins and prevalence of healthcare associated patient to patient transmission of NTM among different CF Care Centers. We will characterize the source(s) of direct or indirect patient-to-patient transmission of NTM within an individual CF healthcare setting.
 
PART B / Water Biofilm Collection: The primary objective is to determine if NTM strains identified in clusters are related to strains isolated from water biofilm sources in the CF healthcare setting. Because hospital and clinic plumbing sources could pose a risk to CF patients, we aim to perform WGS of NTM isolates from healthcare biofilms obtained from CF Centers with NTM clusters among patients to determine if the biofilm isolates are highly related to the isolates recovered from patients.

SECONDARY OBJECTIVES
	
PART A / Epidemiologic Investigation: The secondary objectives are to:
 
 ▪ Assess degree of proximity of subjects in time and/or space. ▪ Compare the relationship between similarity of strains and degree of proximity of subjects. ▪ Model the relationship between the degree of similarity and strains with the proximity and subject characteristic variables. 
PART B / Water Biofilm Collection:

	
The secondary objectives are to:
 
 ▪ Characterize clinically-relevant NTM isolates and healthcare biofilms. ▪ Describe most common biofilm sources within the healthcare setting harboring clinically relevant NTM isolates.
NUMBER OF PARTICIPANTS	
PART A / Epidemiologic Investigation: Unlimited and based on the number of patients identified in an NTM cluster within an individual CF Care Center (prospectively collected data). Two controls will be identified for every subject within a cluster.
 
PART B / Water Biofilm Collection: N/A

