PARTICIPANT SELECTION CRITERIA: Inclusion Criteria	
PART A / Epidemiologic Investigation: Inclusion Criteria:
 
 1. Written informed consent is not required for this retrospective epidemiological study. 2. Diagnosis of CF consistent with the 2017 CFF guidelines. 3. Male or female participant of any age who have a history of NTM species or sub-species collected from expectorated sputum, induced sputum and/or bronchoalveolar lavage and identified by the CO-RDP as falling into a highly-related cluster within a single CF Care Center. 4. Controls subjects are male or female participants of any age who have a history of NTM species or sub-species collected from expectorated sputum, induced sputum and/or bronchoalveolar lavage and identified by the CO-RDP as NOT falling into a highly-related cluster within a single CF Care Center. 
PART B / Water Biofilm Collection: Inclusion Criteria: N/A

PARTICIPANT SELECTION CRITERIA: Exclusion Criteria	
PART A / Epidemiologic Investigation: N/A
 
PART B / Water Biofilm Collection: N/A

CONCOMITANT MEDICATIONS	
Allowed: N/A Prohibited: N/A

PRIMARY ENDPOINT	
PART A / Epidemiologic Investigation: Identification of a shared healthcare-associated source(s) between patients in a CF Care Center.
 
PART B / Water Biofilm Collection:

	Identification of biofilm isolates that are highly related to the isolates recovered from patients.
SECONDARY ENDPOINTS	
PART A / Epidemiologic Investigation: The secondary endpoints are:
 
 ▪ Incidence and prevalence of CF NTM species/subspecies by geographical region. 
PART B/ Water Biofilm Collection: The secondary endpoints are:
 
 ▪ Incidence and prevalence of healthcare-associated water biofilm NTM species/subspecies by geographical region.
EXPLORATORY EVALUATIONS	None
PLANNED INTERIM ANALYSIS	No formal interim analysis involving a data monitoring committee (DMC) is planned.

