
In this study, we are unable to exclude NTM acquisition from direct patient-to-patient contact or via a common environmental source outside the healthcare setting. Evaluation of non-healthcare settings is beyond the scope of this project, but serves as a potential future area of investigation. There may also be a baseline frequency of patient overlap that is not related to transmission events in the healthcare setting that we expect to capture with evaluation of control pairs of subjects. Despite this small sample size, this preliminary data provides insight into the frequency and nature of patient overlap in the healthcare setting and reveals that among CF patients receiving healthcare in the same location, there are opportunities for close direct or indirect contact. In the setting of strict IP&C measures with single patient rooms, healthcare staff gowning and gloving, patients wearing masks, aggressive cleaning procedures between patients, and maintenance of patient-to-patient separation of 6 feet or more, direct and indirect patient overlap should be minimized. However, incidental or unanticipated contacts remain a risk. If patients in fact have no direct or indirect contact, *investigation of the healthcare environment is essential to eliminate a common healthcare-associated environmental source as the point of CF patient NTM acquisition*.

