4 STUDY DESIGN

4.1 Study Overview

PART A / Epidemiologic Investigation:

This study will retrospectively review and collect data from patients with CF and culture positive for an NTM isolate falling in a highly-related cluster, identified by the CO-RDP, within a single CF Care Center. Two control subjects will be identified by the CO-RDP for every subject falling within a cluster. Retrospective epidemiologic data collection and input into REDCap is detailed (**Appendix 1 and 2**). Up to 20 Care Centers will be offered enrollment.

PART B / Water Biofilm Collection:

This study will also collect and analyze water biofilms from a variety of water sources in the healthcare setting including sink faucets, showerheads, shower hoses, ice machines, drinking fountains, and decorative water features. Environmental sampling instructions are detailed (**Appendix 3**).

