15 STATISTICAL METHODS AND CONSIDERATIONS

15.1 General Considerations

For each of the primary and secondary outcomes, biostatistical analysis of the multicenter data will be completed using both qualitative and quantitative approaches. We will identify a set of variables used to assess degree of proximity of subjects in time and/or space. For example, two subjects with neighboring rooms at a hospital would have close proximity, but proximity would be increased for two subjects at a facility that had longer overlap time, relative to a pair of subjects that had shorter overlap. We will explore creating composite measures of quantitative proximity that incorporate multiple variables. Qualitative measures of proximity, such as location type (testing laboratory, patient room) will also be assessed. Several testing approaches will be used to compare the relationship between similarity of strains and degree of proximity of subjects. In the simplest form, descriptive statistics will be computed for proximity variables, for pairs of subjects who are determined to have similar strains versus those who have dissimilar strains, and multivariate or 2-sample t-tests will be performed to test for differences between these groups. More advanced modeling will be performed to determine the relationship between the degree of similarity in strains with the proximity and subject characteristic variables; multiple linear regression will be used when considering continuous strain similarity, while multiple logistic regression will be used when considering subjects with dichotomized (similar/dissimilar) strains to other subjects.

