15.1.1 Data Sets Analyzed

All analyses will be based on the group of subjects that are identified by the CO-RDP as having NTM isolates, defined as highly similar strains at the genomic level, harbored by two or more patients within a single Care Center.

152 Demographic and Baseline Characteristics

The following baseline demographic and clinical characteristics will be reported: age, gender, race, ethnicity, zip code, and NTM sub/species.

153 Analysis of Primary Endpoint

PART A / Epidemiologic Investigation:

The primary endpoint will characterize the origins and prevalence of healthcare-associated patient-to-patient transmission of NTM among different CF Care Centers. We will further characterize the source(s) of direct or indirect transmission of NTM within an individual CF healthcare setting. We will identify a set of variables used to assess degree of proximity of subjects in time and/or space. For example, two subjects with neighboring rooms at a hospital would have close proximity, but proximity would be increased for two subjects at a facility that had longer overlap time, relative to a pair of subjects that had shorter overlap. We will explore creating composite measures of quantitative proximity that incorporate multiple variables. Qualitative measures of proximity, such as location type (testing laboratory, patient room) will also be assessed. Several testing approaches will be used to compare the relationship between similarity of strains and degree of proximity of subjects. In the simplest form, descriptive statistics will be computed for proximity variables, for pairs of subjects who are determined to have similar strains versus those who have dissimilar strains, and multivariate or 2-sample t-tests will be performed to test for differences between these groups. More advanced modeling will be performed to determine the relationship between the degree of similarity in strains with the proximity and subject characteristic variables; multiple linear regression will be used when considering continuous strain similarity, while multiple logistic regression will be used when considering subjects with dichotomized (similar/dissimilar) strains to other subjects.

PART B / Water Biofilm Collection:

The primary endpoint will characterize clinically-relevant NTM found in water biofilms within CF healthcare settings and determine if the biofilm isolates are highly related to isolates recovered from patients.

154 Analysis of Secondary Endpoints

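### Section 15.1.1 bases all analyses on clustered subjects, which by definition leaves out every control that Part A plans as its comparison group

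*Protocol*

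**What the plan says.** Section 15.1.1 (Data Sets Analyzed) sets one rule for the whole study: "All analyses will be based on the group of subjects that are identified by the CO-RDP as having NTM isolates, defined as highly similar strains". The sentence goes on to require that the strain occur in at least two patients of a single Care Center.

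The synopsis (Inclusion Criteria, Part A) describes control subjects as NTM-positive patients "identified by the CO-RDP as NOT falling into a highly-related cluster within a single CF Care Center".

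Controls are part of the design in three places:
- Synopsis, Study Design, Part A: "A control comparison group will also be investigated".
- Synopsis, Number of Participants, Part A: "Two controls will be identified for every subject within a cluster".
- Section 4.1: "Two control subjects will be identified by the CO-RDP for every subject falling within a cluster".

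Their purpose is given in section 1.2, in the discussion of the pilot findings. Patients may cross paths at some background rate, one "that is not related to transmission events in the healthcare setting that we expect to capture with evaluation of control pairs of subjects".

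Sections 15.1 and 15.3 then describe proximity "for pairs of subjects who are determined to have similar strains versus those who have dissimilar strains", test the difference with t-tests, and model it with linear and logistic regression. Section 15.1 gives the scope: "biostatistical analysis of the multicenter data will be completed using both qualitative and quantitative approaches". Sections 15.1 to 15.6 never mention controls.

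**The concern.** Two patients attending the same clinic on the same day is weak evidence of transmission unless one knows how often patients without a shared strain also do so. The control group is there to supply that rate. The only rule on who is analysed covers clustered subjects alone, and a control is by definition not one. A statistician who follows section 15 literally would leave the controls out. One who includes them would depart from the protocol. Either way, the reference group for the comparative analysis could end up being chosen after the overlap data have been seen.

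**Working it through.** The protocol states no sample size or power figure to reproduce. The check is a comparison of definitions followed by simple counts.

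**1. The two groups cannot overlap.** The analysis set (15.1.1) is patients whose strain is highly similar to that of another patient in the same Center. Controls (synopsis) are patients not in such a cluster. A patient who matches only patients of another Center could be a control, but is still outside 15.1.1.

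**2. Share excluded.** With k clustered subjects and two controls each, there are 2k controls among k + 2k = 3k subjects. 2k/3k = 66.7% for any k.

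**3. A Center with one cluster.** Similar pairs are k(k−1)/2: 1, 3 and 6 for k = 2, 3 and 4. Dissimilar pairs under 15.1.1: 0.

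**4. What remains elsewhere.** Section 1.2 reports a pilot Center with six clusters of 2–3 patients: two MAB, one MMAS, two *M. avium*, one *M. intracellulare*. Assume both sizes occur and no patient is in two clusters.
- Five clusters of 2 and one of 3: 13 patients; 13×12/2 = 78 pairs; 5×1 + 3 = 8 within clusters; 70 across clusters.
- One cluster of 2 and five of 3: 17 patients; 17×16/2 = 136 pairs; 1 + 5×3 = 16 within clusters; 120 across clusters.
- Same-species cross-cluster pairs: the three *M. abscessus* clusters (MAB, MAB, MMAS) form 3 pairs of clusters and the two *M. avium* clusters form 1. Each of these 4 gives 2×2 = 4 to 3×3 = 9 patient pairs, so 16 to 36 in all. Over all allowed size combinations the share of cross-cluster pairs runs from 18/81 = 22.2% to 31/93 = 33.3%.
- None of these pairs involves a control. The 2×13 = 26 to 2×17 = 34 planned controls are all excluded.

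**5. Control pairs lost (illustration only).** The protocol does not say how controls are paired.

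| Pairing assumed | k = 2 | k = 3 | k = 4 |
|---|---|---|---|
| Only the two controls of each clustered subject (k) | 2 | 3 | 4 |
| All controls with each other, 2k(2k−1)/2 | 6 | 15 | 28 |
| Clustered with control, k×2k | 8 | 18 | 32 |
| The last two rows together | 14 | 33 | 60 |

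The last three rows assume same-Center controls and full pairing.

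**6. Can a control pair be highly similar?** Section 1.2 reports 26 of 114 MAB patients in highly related clusters, but only 12 of 114 in clusters with care in the same Center. The other 26 − 12 = 14 (14/114 = 12.3%) may, on one reading of the synopsis, qualify as controls. Section 2 adds that an isolate reported as unique may later join a cluster. Control status therefore does not guarantee dissimilarity.

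**7. Same-Center controls (illustration only).** A cluster of 2, 3 or 4 with its controls needs 3k = 6, 9 or 12 patients. Section 1.2 gives 631 banked patients at 92 facilities: 631/92 = 6.9 each. It also gives 79 sequenced Care Centers, and section 1 gives 123 facilities with sequenced isolates: 631/79 = 8.0 and 631/123 = 5.1. Centers with clusters may bank more than the average.

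**The case against.** The strongest defence has four parts.

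- **The primary endpoint is descriptive.** It is the identification of a shared healthcare-associated source, and that can be done from clustered patients alone. This stands. The synopsis also lists the comparison of similarity with proximity as a secondary objective, although section 15.3 places it under the primary endpoint analysis.
- **Dissimilar pairs still exist.** This stands too. A reader might infer that 15.1.1 leaves the similar-versus-dissimilar tests with no reference at all. The documents do not support that: the data are multicenter, a Center may have several clusters, and regression on continuous similarity needs no unclustered group. But every patient in those pairs is clustered, most cross-cluster pairs in the pilot example differ in species, and patients of different Centers have little opportunity to meet in the same setting. They do not supply the baseline described in section 1.2.
- **The wording is loose.** To base analyses on a group is arguably not to restrict them to it, and the synopsis analysis plan carries no cluster-only limit. But the sentence covers all analyses, stands under the heading for data sets, and no sentence in section 15 names the controls.
- **The SAP may define the sets.** It may, but an SAP that included controls would contradict the protocol, and one that followed the protocol would drop them.

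Two cautions are fair. The baseline purpose rests on one sentence in the pilot discussion, though the controls themselves are planned in three other places. And 15.1.1 governs analysis, not collection, so nothing is irretrievably lost if it is corrected in time.

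**Conclusion.** The contradiction is real and should be resolved before any comparative analysis. As written, 15.1.1 removes every control, which is two-thirds of Part A subjects at the stated ratio. That share is the one firm number and rests only on the 2:1 ratio being met. The consequence is limited to the comparison of strain similarity with proximity, which loses its planned unclustered reference; a single-cluster Center contributes no dissimilar pair.

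The counts by pairing scheme and the patients per facility are illustrations, because the protocol states neither the pairing nor whether controls come from the cluster's own Center. A reader might also infer that control pairs can simply be labelled dissimilar. The protocol's own figures speak against that, since exclusion from a same-Center cluster does not rule out a highly similar strain.

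**What to change.** Amend 15.1.1 along these lines: *For Part A the analysis set is all clustered subjects and their CO-RDP-identified controls. Descriptions of clusters use clustered subjects only. Similar-versus-dissimilar comparisons use both groups, with each pair classified by the CO-RDP SNP threshold for its species at a stated data cut, not by control status. For Part B the set remains the clustered subjects, with the environmental isolates.*

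The change works only if these places follow:
- Section 2: the definitions of overlap and point overlap now apply only to patients in the cluster. Extend them to control pairs.
- Appendix 2: pairs are now built only from patients named on the cluster letter. Add steps for control pairs.
- Section 6.2: add the control criterion from the synopsis.
- State which control pairs are abstracted (control with control, clustered with control, or both) and whether controls come from the cluster's own Center. Same-Center controls would best match the baseline purpose, but the protocol does not require them and their availability must be checked.

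The cost is several short text edits and the abstraction of control pairs that section 1.2 already anticipates. No participants are added beyond those planned. Because each pair has its own date range (Appendix 2, step 5), the workload depends on the pairing chosen: from 2, 3 or 4 control pairs for a cluster of 2, 3 or 4, up to 14, 33 or 60 pairs under full same-Center pairing.

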3 STUDY OBJECTIVES

3.1 Primary Objective

PART A / Epidemiologic Investigation:

The primary objective of the epidemiologic investigation is to facilitate implementation of a stepwise process by which individual Centers perform retrospective epidemiologic evaluation of patients identified by the CO-RDP as part of an NTM cluster.

PART B / Water Biofilm Collection:

The primary objective of water biofilm collection is to determine if NTM strains identified in clusters are related to the strains isolated from water biofilm sources in the CF healthcare setting.

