5 CRITERIA FOR EVALUATION

5.1 Primary Endpoint

PART A / Epidemiologic Investigation:

Identification of a shared healthcare-associated source(s) between patients in a Care Center with identical NTM isolates.

PART B / Water Biofilm Collection:

Identification of clinically-relevant NTM isolates and prevalent environmental genotypes with in healthcare setting water biofilms.

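### Section 15.1.1 leaves the planned controls out of every analysis, and section 15.3 promises a prevalence of transmission that Centers enrolled for having a cluster cannot supply

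*Protocol*

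**What the plan says.** **Target.** Section 15.3, Part A: "The primary endpoint will characterize the origins and prevalence of healthcare-associated patient-to-patient transmission of NTM among different CF Care Centers". The synopsis primary objective for Part A: "We will assess the origins and prevalence of healthcare associated patient to patient transmission of NTM among different CF Care Centers". Section 5.1 words the endpoint differently: "Identification of a shared healthcare-associated source(s) between patients in a Care Center with identical NTM isolates".

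**Analysis set.** Section 15.1.1: "All analyses will be based on the group of subjects that are identified by the CO-RDP as having NTM isolates", and it goes on to define these as highly similar strains carried by at least two patients of one Center.

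**Comparison.** Section 15.3 describes proximity variables "for pairs of subjects who are determined to have similar strains versus those who have dissimilar strains". The synopsis (Study Design, Number of Participants) and section 4.1 plan a control group of two per clustered subject. The synopsis inclusion criteria define controls as NTM-positive patients who are not in a same-Center cluster. The Discussion in section 1.2 says that there may be a background level of overlap unrelated to transmission, "that we expect to capture with evaluation of control pairs of subjects".

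**Entry and measurement.** The synopsis and section 2 make Centers eligible once the reference laboratory finds a cluster there. Section 2 defines the toolkit's measurement as overlap: care in the same setting within 24 hours, or use of the same room (a point instance).

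**Secondary endpoints, Part A.** The synopsis names regional incidence and prevalence of NTM species. Sections 5.2 and 15.4 name adherence to infection-control guidelines and points of overlap.

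**The concern.** Two statements in the statistical section do not fit the study that the rest of the protocol describes.

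First, an analysis set confined to clustered patients has no controls in it. Patients who attend the same Center will share clinics and wards whether or not one infected another, so an overlap frequency in clustered pairs can be read only beside the frequency in comparable pairs with unrelated strains. Losing the controls means losing that yardstick.

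Second, a prevalence of transmission needs a denominator that was not chosen on the outcome, and a measurement that identifies transmission. The plan has neither. A figure reported under that name would mainly reflect the rule by which Centers and patients entered.

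**Working it through.** **1. Who is in the analysis set.** Membership of a same-Center cluster is the condition for the 15.1.1 set. Non-membership is the condition for being a control (synopsis inclusion criteria). The two exclude each other, so the set contains no controls. With k clustered patients and 2 controls each, 2k of 3k planned subjects are dropped: 2k/3k = 2/3.

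**2. What is left to compare.** Pairs within a cluster of k patients: k(k−1)/2. For k = 2, 3, 4 this gives 1, 3, 6, which reproduces the counts in Appendix 2.

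- *One-cluster Center, 15.1.1 as written:* all pairs are within the cluster, so there are 1, 3 or 6 similar pairs and 0 dissimilar pairs.
- *Six clusters,* as in the preliminary Center of section 1.2, where clusters had 2 to 3 patients. If all had 2: 12 patients, 12×11/2 = 66 pairs, 6 similar, 66−6 = 60 dissimilar. If all had 3: 18 patients, 18×17/2 = 153 pairs, 18 similar, 153−18 = 135 dissimilar. This assumes that no patient is in two clusters and that cross-cluster pairs count as dissimilar.
- *One-cluster Center with controls kept:* 3k(3k−1)/2 = 15, 36, 66 pairs, hence 14, 33, 60 dissimilar pairs. Of these, 2k(2k−1)/2 = 6, 15, 28 are control with control. This assumes that controls attend the same Center and that no pair involving a control is similar.

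The same-Center assumption matters because no passage states it. Nor does the rest of the protocol provide for controls in practice. Section 6.2 has no control criterion (and no cluster criterion). The overlap definition in section 2 speaks only of patients in the cluster. The pairing steps in Appendix 2 start from the patients named in the cluster letter.

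**3. Whether a prevalence can be had.** Section 15.3 gives no figure for it. The nearest is in section 1.2: 12 of 114 *M. abscessus* ssp. *abscessus* patients were in a same-Center cluster, 12/114 = 10.5%, which agrees with the printed 11% (exact 95% interval 5.6% to 17.7%). That is genomic clustering among sequenced patients, not transmission.

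In the enrolled sample, the clustered share is fixed in advance: 100% of Centers have a cluster, and clustered patients are 100% of subjects under 15.1.1 or 1/3 with controls. To show how this carries through, suppose that a share q of clustered patients acquired NTM by healthcare transmission and no other patient did (q from 10% to 100%, an assumption):

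| Base | Formula | q = 10% | q = 100% |
|---|---|---|---|
| Sequenced patients | q × 12/114 | 1.1% | 10.5% |
| 15.1.1 set | q | 10% | 100% |
| With two controls each | q/3 | 3.3% | 33.3% |

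The same truth gives figures that differ by 114/12 = 9.5 times between the first two rows, through selection alone. This is an illustration; the protocol does not propose to report any of these rows.

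Nor is q observed. The toolkit abstracts clinic, hospital and research visits and returns overlap. Section 1.2 concedes: "we are unable to exclude NTM acquisition from direct patient-to-patient contact or via a common environmental source outside the healthcare setting".

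**4. Secondary endpoints.** The synopsis item (species by region) appears in neither 5.2 nor 15.4 for Part A, and their two items appear nowhere in the synopsis list. All enrolled subjects are NTM-positive, so they cannot supply an incidence or prevalence of NTM among CF patients.

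**The case against.** **Prevalence may be meant descriptively.** The text says among different Centers and claims no national figure; a reader could take it as how often the event is found in the Centers investigated. That is fair, and it lies close to the quantity proposed below. It does not rescue the word transmission, since what is found is overlap.

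**The concession about outside sources stands in a discussion of preliminary data.** Parts of section 1.2 are not available, so whether it speaks of the pilot or the whole study cannot be settled. Little depends on it: the next sentence puts non-healthcare settings beyond the project's scope, and the toolkit collects no data on them.

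**The missing prevalence estimator may be in the SAP.** Correct, and its absence from 15.3 is not used as evidence here. The argument rests on how Centers and patients enter and on what is measured.

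**15.1.1 does not abolish the comparison.** A reader might infer that no dissimilar pairs remain anywhere. That goes too far: the six-cluster Center keeps 60 to 135, and pooling Centers adds more. But every patient in a cross-cluster pair was selected for being in a cluster, so these are not the controls that section 1.2 relies on. Patients of different Centers have little opportunity to overlap at all and give no baseline either.

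**Species prevalence can mean distribution among isolates.** It can, and the reference laboratory's data would support that. The mismatch with 5.2 and 15.4 remains.

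**Conclusion.** The point holds in three parts. (1) Section 15.1.1 contradicts the control design; followed literally, it removes two thirds of planned subjects and leaves a one-cluster Center with no dissimilar pair. (2) Section 15.3 and the synopsis objective name a quantity that this sample cannot estimate. (3) The synopsis and body disagree on the Part A secondary endpoints. Parts 1 and 3 rest on the text alone. Part 2 rests on the entry rule and on overlap being the measurement; the 9.5-fold figure depends on the assumptions stated with it and only illustrates the direction.

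Two further inferences are tempting and not supported. One is that Part B cannot yield an incidence because each outlet is sampled once: the documents give no number of sampling rounds. The other is that section 3.1 already states the narrower target: its aim, that "individual Centers perform retrospective epidemiologic evaluation of patients identified by the CO-RDP as part of an NTM cluster", describes a process and names no quantity. Section 5.1 and the control pairs are the better support, and even 5.1 is the identification of a source, so the proportion proposed below has to be written in.

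The text should be corrected before analysis. The design itself need not change.

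**What to change.** 1. **Section 15.1.1:** include the planned controls in the Part A comparative analyses, and state that they come from the same Center as the clustered subjects with whom they are compared. Align section 6.2, the overlap definition in section 2 and the Appendix 2 pairing steps so that they cover controls.
2. **Section 15.3 and the synopsis primary objective:** replace the prevalence of transmission with the proportion of clustered pairs in enrolled Centers that show a healthcare overlap, or a point instance of overlap, beside the same proportion in control pairs. Say whether control pairs are control with control or include clustered patients. State that the result does not estimate how common transmission is. With pairs as the unit, a four-patient cluster counts six times; the text should acknowledge this.
3. **Synopsis Part A secondary endpoint:** reconcile it with 5.2 and 15.4. If it is kept, describe it as the species distribution among the reference laboratory's isolates.

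**Cost.** The changes are to wording, and the control group is already planned. Two consequences should be accepted openly. The quantity is narrower and silent on Centers without a detected cluster. Same-Center controls may also be scarce: one cluster of 2 to 4 patients needs 4 to 8, and a Center with 12 to 18 clustered patients needs 24 to 36, so the text should say what happens when fewer are available.
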